**Assessing Home Food Environment and Diabetes Self-management Among Adult Type 2
Diabetes Patients**

ClinicalTrials.gov identifier: NCT03039569

Date: June 1, 2018

Study Protocol

The current research project was approved by the University of Nebraska in Lincoln, Nebraska and the Methodist Health System in Omaha, Nebraska. Study participants were recruited from the Methodist Health System Center for Diabetes and Nutritional Health in Omaha, Nebraska. The center is an ambulatory outpatient clinic for treatment of patients with diabetes. Inclusion criteria were adults aged ≥ 30 years with Type 2 diabetes; self-reported hemoglobin A1C $>6.5\%$, having a cellular phone with the ability to receive text messages and English speaking.

A quasi experimental design was used in this pilot study due to timeframe restraints. Eligible participants who came into the clinic for outpatient diabetes management care were identified and approached. A survey regarding participants' demographics and, relevant risk factors for Type 2 diabetes was completed by all the participants (intervention and control group) at baseline.. The intervention group started approximately two months earlier than the control group. Participants in both the intervention and control groups received the usual care for Type 2 diabetes including an initial visit from either a Registered Dietitian or Certified Diabetes Educator and follow-up visits. The intervention group received three messages weekly (on Mondays, Wednesdays and Fridays) for 12 weeks based on topics regarding nutrition education and diabetes self-care information and skills. The messages were different each week during the first six weeks (Weeks 1 to 6) and repeated during the remaining weeks (Weeks 7 to 12). The messages consisted of strategies to increase fruits and vegetables and reduce high-fat and sugary foods intakes and to improve diabetes self-care skills, increasing physical activity, and increase awareness of CVD risk perception and knowledge (Table X). The text messages were derived from the topics and guidelines provided by the American Association of Diabetes Educator

(AADE) including “Reducing Risks”, “Monitoring”, “Healthy Coping”, “Problem Solving”, “Taking Medication”, “Healthy Eating”, and “Exercise”. Each text message included the novel approach of including a link to a specific AADE7 topic and handout that allowed participants to open and retrieve the specific AADE7 information. Unidirectional text messages were sent by the project investigators to the participants in the intervention group via a computer-based text messaging program through a password protected computer which was only accessed by the investigators. Participants’ phone numbers used for text message intervention was kept private, and they were advised not to reply to the text message. If a participant had a medical concern about his/her diabetes, he/she was advised to contact his/her physician or call 911. The control group (usual care group) did not receive text messages. Participants in both the intervention (text messaging + usual care) and control group completed surveys regarding their awareness of CVD risk, diabetes self-care activities, dietary intake, and physical activity at baseline and at 12-week follow-up (conclusion of the intervention). Further, the participants in the intervention group completed a survey to evaluate their satisfaction with receiving text messaging for managing diabetes after the text messaging intervention was concluded. A \$25 gift card were offered to participants in both intervention and control groups.

Statistical Analysis

Primary analyses were based on participants in the intervention group or control group at the time of the initiation of the intervention (baseline) regardless of adherence status (intent-to-treat analysis). Baseline characteristics were calculated using descriptive statistics and compared between groups using t test for continuous variables and Chi-square analyses for categorical variables. Treatment effects were evaluated by assessing the differences in the outcome variables from baseline to the 12-week follow-up between participants in the intervention group and the

control group using Proc Glimmix procedure. The model included the intercept, time effect (baseline and follow-up), and interactions between treatment groups (intervention and control groups) and the time effect (the absolute treatment effect). Least squares means were calculated for each time and treatment combination and the differences were calculated between treatments within each time point. Estimates of the absolute treatment/intervention effect were determined as follow: [(intervention group follow-up) – (intervention group baseline)] – [(control group follow-up) – (control group baseline)]. To provide perspective on the magnitude of the treatment/intervention effects, we also calculated proportional treatment/intervention effects, defined as (absolute treatment/intervention effect/intervention group baseline) × 100% (e.g., a proportional effect of 55% would mean a 55% increase in the intervention group relative to the control group). The analyses were repeated after the adjustment for unbalanced baseline characteristics (race/ethnicity, education) and the results did not change materially. SAS software (SAS Institute, Cary, NC) was used for analyses. All tests were 2-sided, and $P < 0.05$ was considered statistically significant.

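### The intent-to-treat statement does not cover missing 12-week surveys, and under the model as listed, outcome-related loss that differs between groups can bias the difference-in-differences

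*Combined protocol and SAP*

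**What the plan says.** The primary analyses take participants in the group they were in when the intervention started, "regardless of adherence status (intent-to-treat analysis" (Statistical Analysis). The outcomes are self-reports: both groups "completed surveys regarding their awareness of CVD risk, diabetes self-care activities, dietary intake, and physical activity at baseline and at 12-week follow-up" (Study Protocol). There is no assessment between those two.

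The model is run in Proc Glimmix and described as follows: "The model included the intercept, time effect (baseline and follow-up), and interactions between treatment groups (intervention and control groups) and the time effect". Then "Least squares means were calculated for each time and treatment combination", and the treatment effect is the change in the intervention group minus the change in the control group. The proportional effect divides that by the intervention group's baseline. The one repeat analysis adjusts for race/ethnicity and education.

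The combined protocol and SAP gives no group sizes, no number lost, no missing-data assumption or method, and no sensitivity analysis for loss. It neither states nor excludes a subject effect or a repeated-measures covariance.

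**The concern.** Consider a participant who leaves at week 5. By the stated analysis set this person is included, with a baseline record and no follow-up record. If the model has only the listed terms, the group's change compares everyone at baseline with those who answered at week 12. Part of the estimated effect can then be a change in who responded rather than a change in behaviour. The same error enters the proportional effect, because the absolute effect is its numerator.

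The label adds to the problem. A reader who sees intent-to-treat will take it that withdrawal has been dealt with. As written, the reader cannot tell whether the result is a full-set comparison of cell means, a likelihood-based repeated-measures analysis or a completer analysis. These can give different estimates from the same data.

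**Working it through.** There is no figure in the plan to reproduce. All loss rates, correlations and gaps below are assumptions. Effects are intervention minus control, in units of the outcome SD, and the true effect is 0 unless stated.

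**Step 1: where a lost participant counts.** An intercept, a time effect and group-by-time terms, summarised by one least squares mean per time and group, give four free means. With no within-subject term, these are the four observed cell averages. A participant with only a baseline survey enters one cell.

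**Step 2: the bias.** In group g let d be the proportion lost, δ the baseline mean of completers minus that of those lost, and ρ the correlation between visits. Let loss depend on baseline only. Completers then start dδ above the full group, and their follow-up mean is ρdδ too high.

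- Listed terms only: bias = ρ(d_I δ_I − d_C δ_C)
- Completers' change scores: bias = −(1 − ρ)(d_I δ_I − d_C δ_C)
- Follow-up predicted from baseline within each group: bias = 0

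**Step 3: numbers with δ about 0.5 in both groups.** For 10% lost in intervention and 30% in control, at ρ = 0.5: 0.5 × 0.5 × (0.10 − 0.30) = −0.050. At ρ = 0.7: 0.7 × 0.5 × (−0.20) = −0.070. Simulation with 1,000,000 per group (logistic loss, slope 0.5 on baseline, δ from 0.47 to 0.50) agrees:

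| Loss, intervention vs control | ρ | Listed terms | Completers | Predicted from baseline |
|---|---|---|---|---|
| 10% vs 20% | 0.5 | −0.022 | +0.024 | +0.001 |
| 10% vs 20% | 0.7 | −0.030 | +0.016 | +0.002 |
| 10% vs 30% | 0.5 | −0.046 | +0.050 | +0.002 |
| 10% vs 30% | 0.7 | −0.066 | +0.028 | 0.000 |
| 5% vs 40% | 0.5 | −0.084 | +0.081 | −0.002 |
| 5% vs 40% | 0.7 | −0.114 | +0.050 | +0.001 |

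**Step 4: direction.** A separate simulation (2,000,000 per group, slope 1, so a larger δ) put the heavier loss in the intervention group, 30% vs 10%. The listed terms gave +0.05, +0.08 and +0.11 at ρ = 0.3, 0.5 and 0.7. The sign would also reverse if those lost started higher than completers.

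**Step 5: unequal loss is neither sufficient nor necessary.** If loss is completely at random, δ = 0 and the bias is 0; simulation at 30% vs 10% and 40% vs 10% gave 0.00. Equal loss of 20% with the same selection in both groups also gave 0.00. Equal loss of 20% with opposite baseline selection gave 0.10, 0.17 and 0.24 at the three correlations.

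**Step 6: what a within-subject term does.** In the Step 4 setting, fitting the within-subject correlation by maximum likelihood brought the bias to 0.00. As a check, model fits at ρ = 0.5 (3,000 per group, 12 replicates) gave 0.089 (SE 0.008) with no subject term and 0.010 (SE 0.006) with a random intercept.

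**Step 7: what it does not do.** If loss depends on the 12-week value itself (30% vs 10%), the listed terms gave 0.16, and the within-subject fit still left 0.15, 0.13 and 0.09. Put another way, if those lost changed 0.5 SD less than similar completers, an error of 0.5 × 0.20 = 0.10 SD remains at 10% vs 30%.

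**The case against.** Proc Glimmix is a mixed-model procedure, and the listed terms may be the fixed effects only. With a subject effect, the baseline-dependent bias, which covers every entry in the table, disappears. This stands: the point is conditional on the model as listed, and stating the within-subject term is the simplest repair. It does not remove the point, because no such term is stated and loss related to the 12-week value would remain.

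No loss is documented. The Study Protocol section says that both groups completed both surveys. That does not establish complete follow-up, but loss could have been nil or trivial.

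The bias may be small beside sampling error. Assuming 25 to 50 per group and ρ = 0.5, the standard error of the difference-in-differences is √(4 × 0.5 / n), or 0.28 to 0.20 SD, so 0.05 SD is about 0.2 of a standard error. This also stands, though a bias does not average out and the interval does not show it.

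A reader might infer that the design makes unequal loss likely: the intervention group was sent 3 × 12 = 36 texts, while "The control group (usual care group) did not receive text messages", the groups started about two months apart, and allocation was not randomised. The document does not support going that far. The texts were one-way and participants were advised not to reply. Both groups had usual-care follow-up visits, the same survey times and the gift card. Differential loss is plausible, not shown.

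**Conclusion.** The point holds in conditional form. The intent-to-treat statement leaves missing 12-week surveys unaddressed. Under the listed terms with no within-subject term, outcome-related loss that differs between groups in amount or kind can bias both the absolute and the proportional effect. At an assumed 10% vs 30% baseline-dependent loss, with those lost starting about 0.5 SD below completers and a visit correlation of 0.5 to 0.7, the bias is about 0.05 to 0.07 SD, in a direction set by which group loses more. At 10% vs 20% it is 0.02 to 0.03 SD.

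Two stronger readings are tempting and unsupported. One is that unequal loss by itself biases the estimate; Step 5 shows that it does not, and that equal loss is no guarantee either. The other is that the reported effect is wrong. With no loss figures and no statement on a subject effect, the existence, size and direction of any bias are unknown.

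**What to change.** 1. Analyse all participants with a baseline survey in their group. Either fit both visits by likelihood in Proc Glimmix with a stated within-subject term (subject random effect or unstructured covariance), or multiply impute missing 12-week outcomes separately by group from baseline outcome, race/ethnicity and education, and compute the difference-in-differences on the imputed data. State that both rest on missing at random.
2. Add a sensitivity analysis that shifts the imputed 12-week values by 0 to 0.5 SD in the unfavourable direction, in each group separately, and report the shift at which the conclusion changes. For scale, 0.5 SD in a group that lost 30% moves its follow-up mean by 0.5 × 0.30 = 0.15 SD.
3. Report 12-week survey returns by group, with baseline values of those who did and did not return the survey.
4. If only participants with both surveys were analysed, call it a completer analysis and drop the intent-to-treat label. Restricting to completers is not a repair: in the table it is biased in the opposite direction.

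The study is complete, so no further data collection is proposed. The cost is revised wording and a short SAS re-analysis of data already held, slightly wider intervals and, if loss was high, possibly a less favourable label. In a small pilot, imputation by group may be unstable, which favours the likelihood route for the primary result.

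### The listed Glimmix model has no within-person term for the paired surveys; if fitted as listed, with positive within-person correlation, the treatment-effect standard error is too large

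*Combined protocol and SAP*

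**What the plan says.** The Study Protocol section has participants in both arms complete the outcome surveys "at baseline and at 12-week follow-up (conclusion of the intervention". Every outcome is therefore measured twice on the same person.

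The Statistical Analysis section bases the treatment effect on "assessing the differences in the outcome variables from baseline to the 12-week follow-up". It describes the comparison with the "control group using Proc Glimmix procedure. The model included the intercept, time effect (baseline and follow-up), and interactions between treatment groups" and time. It adds that "Least squares means were calculated for each time and treatment combination". The sentence opening "Estimates of the absolute treatment/intervention effect were determined as follow" defines the effect as the change in the intervention arm minus the change in the control arm. Tests are two-sided at the 5% level.

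A second analysis is reported in one sentence: "The analyses were repeated after the adjustment for unbalanced baseline characteristics (race/ethnicity, education) and the results did not change materially".

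Neither section mentions a random effect, a subject identifier, a repeated-measures or residual covariance, or a robust variance. No outcome distribution or link is stated.

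**The concern.** The listed terms fix the four cell means (two arms at two times). They say nothing about how one person's two answers are related, and that relation determines the standard error of a change. Naming the procedure does not settle the matter: Glimmix allows for within-person dependence only when the user specifies it. Given the listed terms alone, it treats all records as independent.

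A person who scores high at baseline will usually score high again 12 weeks later. Taking the change removes this shared part, so a correct analysis has a smaller variance than one that treats the records as unrelated. If the shared part is ignored, the standard error of the treatment effect is overstated and its P-value is too large. In a pilot, the price is a real effect that may go undetected. Readers are also left unable to tell which standard error lies behind the reported tests.

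**Working it through.** **Inputs from the document.** Two surveys per person; mean terms of intercept, time and group-by-time; a difference-in-differences effect; two-sided 5% tests. The plan gives no sample size, standard deviation, correlation, dropout or power, so it has no figure to reproduce. Everything below that uses rho, missingness or a reference power is an assumed range.

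**Mean model.** Intercept, time and group-by-time have rank 4 for the four cells. All four means, and so the contrast, are estimable without a separate group term. Only the variance is in question.

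**Complete pairs.** Let s² be the outcome variance at both times, rho the within-person correlation, and n1 and n2 the arm sizes.

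- Variance as listed: 2s²(1/n1 + 1/n2)
- Correct variance: 2s²(1 − rho)(1/n1 + 1/n2)
- Ratio of standard errors: 1/√(1 − rho), free of sample size and allocation. At rho = 0.5 this is 1/√0.5 = 1.414.
- True size of the 5% test: 2·P(Z > 1.96/√(1 − rho)). At rho = 0.5: 2·P(Z > 2.772) = 0.0056.
- Power for an effect that the correct analysis detects with an assumed 80%: P(Z > 1.96/√(1 − rho) − 2.80). At rho = 0.5: P(Z > −0.03) = 0.51.

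**Missing follow-up.** Suppose a fraction d of each arm is missing completely at random at 12 weeks, and the baseline records stay in. Per arm of n people, the listed model takes the variance of the change in means as (s²/n)[1/(1 − d) + 1]. The true value for the same estimate is (s²/n)[1/(1 − d) + 1 − 2·rho]. At d = 0.2 and rho = 0.5 the ratio of standard errors is √(2.25/1.25) = 1.34.

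| If fitted as listed | rho 0.3 | rho 0.5 | rho 0.7 |
|---|---|---|---|
| SE ratio, complete pairs | 1.20 | 1.41 | 1.83 |
| True size of 5% test, complete pairs | 1.9% | 0.56% | 0.035% |
| Power where the correct analysis has 80%, complete pairs | 68% | 51% | 22% |
| SE ratio, 20% missing | 1.17 | 1.34 | 1.63 |
| True size of 5% test, 20% missing | 2.2% | 0.85% | 0.14% |

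**Simulation check.** Normal outcomes were simulated with 20/20, 40/40 and 40/20 per arm, 4,000 runs per setting. At rho 0.3, 0.5 and 0.7 the SE ratios were 1.18–1.20, 1.39–1.41 and 1.81–1.83 with complete pairs, and 1.16–1.18, 1.29–1.34 and 1.60–1.63 with 20% missing. A separate simulation with 30 per arm, complete pairs and 100,000 runs gave sizes of 1.9%, 0.63% and 0.05% as listed, against 4.9%, 5.1% and 5.1% with the pairing respected.

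**Sign.** At rho = 0 the ratio is 1. At rho = −0.2 it is 1/√1.2 = 0.91 and the size is 7.4%. The direction therefore depends on positive correlation.

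**The case against.** The strongest reply is that no error has been shown. Every item in the model sentence is a mean-model term, and a list of fixed effects does not rule out a covariance structure. Glimmix is a mixed-model procedure, so the description is consistent with a participant term that was fitted and not mentioned. This stands. A reader might infer that the reported standard errors are wrong; the document does not support that. What it supports is that the model, followed as written, gives the wrong standard error, and that nothing elsewhere in the text corrects it.

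The second reply is that the fault is on the safe side. With positive correlation this also stands. A reader might suspect false positive treatment effects, but under that condition the test rejects too seldom. The cost is lost power, which still matters in a pilot.

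The third reply is that every size is assumed and that complete pairs are the worst case. The primary analysis includes everyone in an arm at baseline, and the share with a 12-week survey is not given. Missing follow-up shrinks the inflation without reversing it: at 40% missing, the same formula gives 1.14, 1.26 and 1.45. The complete-pairs figures should not be read as this trial's figures.

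Two other inferences fail. Leaving out a group main effect is not an error, as the rank check shows. And where the plan says "the differences were calculated between treatments within each time point", those contrasts compare different people, so ignoring the pairing does not inflate their standard errors in this way.

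**Conclusion.** The concern holds in conditional form. As written, the plan gives a model for paired data with no allowance for the pairing, in both the main and the adjusted analysis. If that model was fitted and rho is positive, the standard error of the treatment effect is overstated by about 20% to 83% for rho between 0.3 and 0.7 with complete pairs, or about 17% to 63% with 20% of follow-ups missing. The test is conservative, so significant treatment effects stand on this point and non-significant ones may be understated. With complete pairs the estimate itself does not change.

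The closed forms assume a continuous outcome with equal variance at both times, and rho is not in the document. In the adjusted analysis the relevant rho is the correlation that remains after the covariates. Whether a participant term was used is unknown, so this is a point to be settled, not proof of a wrong analysis.

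**What to change.** In the Statistical Analysis section, specify a within-person covariance with participant as the subject, for both the unadjusted models and those adjusted for race/ethnicity and education.

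- **Continuous outcomes:** an unstructured 2×2 residual covariance, with a small-sample degrees-of-freedom method.
- **Any non-normal outcome:** a marginal covariance or a participant-clustered variance with a small-sample correction, with the distribution and link stated. A marginal form keeps the group means from which the absolute and proportional effects are built.

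If such a term was already fitted, the cost is one corrected sentence. If not, it is one or two SAS statements per model, a refit of each outcome, and revised standard errors and P-values. Where follow-up is incomplete, the estimates may shift a little as well. The document reports the analyses as already done, so the results would need to be reissued in that case. No new data are needed.

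### Does the 55% example misdescribe the proportional effect by calling it an increase relative to the control group?

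*Combined protocol and SAP*

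**What the plan says.** The Statistical Analysis section first defines the absolute effect as the intervention group's change from baseline to follow-up minus the control group's change. It then introduces a proportional effect, "defined as (absolute treatment/intervention effect/intervention group baseline) × 100" percent, to give a sense of magnitude, and closes the same sentence with an illustration: "e.g., a proportional effect of 55% would mean a 55% increase in the intervention group relative to the control group". The section also states: "Least squares means were calculated for each time and treatment combination". It adds that the two groups are compared at each time point.

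Two statements in the Study Protocol section bear on the point: "A quasi experimental design was used in this pilot study due to timeframe restraints" and "Participants in both the intervention and control groups received the usual care for Type 2 diabetes".

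**The concern.** The denominator of the index is the intervention group's own baseline mean; no control-group level appears in it. Yet the illustration compares with the control group and does not say what the 55% is a percentage of. Someone who reads only the illustration could conclude that the intervention group finished 55% above the control group.

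That conclusion is assured only if both groups start at the same mean and the control group does not move. Allocation was not randomised, and the section reports imbalance in race/ethnicity and education ("The analyses were repeated after the adjustment for unbalanced baseline characteristics (race/ethnicity, education"), so equal outcome baselines cannot be presumed. Both groups received active usual care, so a static control group cannot be presumed either. At stake is how a reader of the results understands the size of the effect. No hypothesis test is involved.

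**Working it through.** **Inputs.** Write I0, I1 for the intervention means and C0, C1 for the control means, at baseline and follow-up. From the Statistical Analysis section:

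- absolute effect D = (I1 − I0) − (C1 − C0)
- proportional effect P = 100 × D / I0

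The 55% is hypothetical, and the documents give no outcome means. It cannot be reproduced from trial data, and every mean below is an assumption.

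**Step 1: a case that gives 55%.** Take I0 = 20 and D = 11. Then P = 100 × 11/20 = 55%, whatever the control values.

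**Step 2: the possible readings.**

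- R1, increase net of the control change, as a share of the intervention baseline: 100 × D / I0
- R2, level above control at follow-up: 100 × (I1/C1 − 1)
- R3, ratio of changes: 100 × [(I1/I0)/(C1/C0) − 1]
- R4, difference of percent changes: 100 × [(I1 − I0)/I0 − (C1 − C0)/C0]

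| Intervention | Control | R1 | R2 | R3 | R4 |
|---|---|---|---|---|---|
| 20→31 | 20→20 | 55% | 55% | 55% | 55% |
| 20→33 | 20→22 | 55% | 50% | 50% | 55% |
| 20→31 | 40→40 | 55% | −22.5% | 55% | 55% |
| 20→36 | 40→45 | 55% | −20% | 60% | 67.5% |

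R1 equals 55% in every row because it is the formula itself. The other three depend on the means.

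**Step 3: how far the other readings can drift.** Assume I0 = 100, D = 55, C0 from 80 to 120, and a control change of −20% to +20%, with I1 = 155 + (C1 − C0).

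- R2: the lowest value is at C0 = 120, C1 = 144, I1 = 179, where 179/144 − 1 = 24.3%. The highest is at C0 = 80, C1 = 64, I1 = 139, where 139/64 − 1 = 117.2%.
- R3: from 1.71/1.20 − 1 = 42.5% to 1.39/0.80 − 1 = 73.75%.
- R4: from 31 + 20 = 51% to 79 − 20 = 59%.

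With equal baselines and a control change of ±10%, R2 runs only from 165/110 − 1 = 50.0% to 145/90 − 1 = 61.1%.

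**Step 4: when the readings agree with the formula.** With p = P/100:

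- R1: always.
- R2: when (1 + p)(I0 − C0) = p(C1 − C0). Equal baselines with an unchanged control group satisfy this; other solutions are coincidences.
- R3: when C1 = C0, or when C0 = (1 + p) × I0. For example, control 110→132 and intervention 100→132 give D = 32 − 22 = 10, so P = 10%, and 1.32/1.20 − 1 = 10% although control rose by 20%.
- R4: when C0 = I0 or C1 = C0.

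**The case for a change.** The best case for a change is that the illustration exists only to explain the index, and it leaves out the one fact a reader needs. The section also sets up between-group contrasts at each time point, so a follow-up comparison is already in view when the reader meets the example. The conditions that would make that reading correct are not assured here. Naming the denominator would cost one sentence.

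Part of this stands: the wording is loose, and it is wrong if read as a level above control. The rest does not carry it to a change in the plan.

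- The definition, denominator included, comes immediately before the illustration in one sentence, after the absolute effect has been defined as a difference between two changes. In that position, R1 is a natural reading and it is exact.
- The follow-up contrast that R2 would need is calculated separately, as are the four group-by-time means. Nothing says they will be withheld.
- The striking possibility of an index of 55% with no rise in the intervention group requires control to fall by 55 points. On a control baseline of 80 to 120 that is a fall of 55/120 = 46% to 55/80 = 69%, well beyond the ±20% assumed above.
- Randomisation would not remove the issue, since it guarantees neither identical sample baselines nor a static control group.
- A further caution, that percentages mislead for scores without a true zero, has nothing to attach to: the documents describe no instrument or scoring.

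**Conclusion.** No change follows. The formula is coherent, and the illustration agrees with it when read as an increase net of the control group's change. Only the literal reading, as a level above control, fails. The size of that failure rests wholly on assumed means: 24.3% to 117.2% against a nominal 55% at the corners of the wide grid, and 50.0% to 61.1% in the milder case. The documents report no outcome imbalance that would point to the wider range.

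The example is a hypothetical parenthesis attached to a descriptive index in a pilot study. The plan attaches no test to the index, and rewording the example would leave every estimate, percentage, P value and conclusion as it is. Whoever writes up the results may name the denominator as a matter of style, but the plan loses nothing as it stands.

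### If race/ethnicity and education entered only as main effects, finding no material change after adjustment says little about whether they explain the treatment effect

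*Combined protocol and SAP*

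**What the plan says.** The Study Protocol section states: "A quasi experimental design was used in this pilot study due to timeframe restraints". The groups also started about two months apart.

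Under Statistical Analysis, baseline characteristics were "compared between groups using t test for continuous variables and Chi-square analyses for categorical variables". The effect is a contrast of changes: "Treatment effects were evaluated by assessing the differences in the outcome variables from baseline to the 12-week follow-up" were compared between the groups. The model is described as follows: "The model included the intercept, time effect (baseline and follow-up), and interactions between treatment groups (intervention and control groups) and the time effect". The group-by-time term is labelled the absolute treatment effect. The effect formula subtracts each group's own baseline from its own follow-up and then takes the difference between groups.

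The same section adds: "Least squares means were calculated for each time and treatment combination and the differences were calculated between treatments within each time point".

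On confounding by the imbalances it acknowledges, it says only: "The analyses were repeated after the adjustment for unbalanced baseline characteristics (race/ethnicity, education) and the results did not change materially".

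No covariate-by-time term is mentioned. The section gives no distribution or link, no number of participants with both visits, no adjusted estimate and no definition of a material change.

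**The concern.** In a non-randomised comparison, that one sentence is the document's only assurance that the two named imbalances do not account for the treatment effect. A reader will take it as a robustness check.

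A DID already removes anything that shifts a participant's baseline and follow-up values equally. What can still bias it is a characteristic that is unbalanced between groups and also predicts how much people change. A covariate main effect only shifts level, so it addresses what the DID has already removed and not what remains. If that was the adjustment, the DID would look stable almost equally often with and without confounding of change.

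**Working it through.** **No figure to reproduce.** The documents give no sample size, SD, dropout, size of imbalance or adjusted estimate. The first step below is algebra; the rest is illustrative, with all inputs assumed.

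**1. Why a main effect cancels.** Let m(g,t) be the mean for group g at visit t, X a covariate measured once, and b its main effect:

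Y(i,t) = m(g,t) + bX(i) + error.

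The change for participant i is m(g,1) − m(g,0) + difference in errors. The term bX(i) has gone. With an identity link, complete pairs and a separate mean for each group and visit, the estimated DID is the difference in mean change, with or without X.

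If X also predicts change by an amount c, then

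expected DID = true effect + c × (mean X in intervention − mean X in control).

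Only a model that lets X act on change can remove the second term.

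**2. Bias left in the DID.** Assumed: SD 1, within-person correlation 0.5, true effect 0, 40 per group. Education is binary, 70% vs 40%, adding 0.5 SD to level and a further 0.5 SD to change. Race/ethnicity is binary, 30% vs 15%, with no effect. Expected bias is 0.5 × (0.70 − 0.40) = 0.15 SD. Mean simulated DIDs:

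| Setting | Unadjusted | Main effects | Covariate × time |
|---|---|---|---|
| Complete pairs | 0.149 | 0.149 | 0.000 |
| 30% missing at random | 0.148 | 0.148 | −0.004 |
| 30% missing, depending on education (15% vs 45%) | 0.131 | 0.140 | −0.007 |
| Logit link (log odds; education adds 0.8 to level and 0.8 to change) | 0.186 | 0.198 | −0.017 |

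With complete pairs, the largest difference between the first two columns in any data set was 1×10⁻¹⁴, which is rounding. ANCOVA on follow-up gave 0.002 and inverse-probability weighting 0.001. A separate calculation at 50 per group, with an expected bias of 0.5 × (0.7 − 0.3) = 0.20 SD, gave 0.193, 0.193 and −0.024.

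**3. What a finding of no material change is worth.** Take it to mean a DID shift below 0.05 SD. Probability of seeing it at 40 per group, without vs with confounding:

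| Follow-up | Main effects | Covariate × time |
|---|---|---|
| Complete | 100% vs 100% | 47% vs 14% |
| 15% missing | 99.9% vs 98.7% | 43% vs 17% |
| 30% missing | 96.9% vs 91.9% | 39% vs 18% |

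For the logit link (shift below 0.25 SE), main effects gave 99.5% vs 96.3%. Under main effects the ratio of the two probabilities is close to 1 throughout.

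**4. How large the bias might be.** Suppose unbalanced means P < 0.05 on the Chi-square comparison. For a binary covariate with pooled proportion p and n per group, the smallest such gap is 1.96 × √(2p(1−p)/n). At p = 0.5 this is 31, 22 and 18 percentage points for n = 20, 40 and 60.

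The DID has standard error √(4(1−ρ)/n), where ρ is the within-person correlation. Dividing, n cancels:

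bias/SE = 1.96 × √(p(1−p)) × c / √(2(1−ρ)).

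- p = 0.5, c = 0.2, ρ = 0.3: 1.96 × 0.5 × 0.2 / √1.4 = 0.17, false-positive rate 5.3%.
- p = 0.5, c = 0.5, ρ = 0.7: 1.96 × 0.5 × 0.5 / √0.6 = 0.63, false-positive rate 9.7%.
- p = 0.2, same two cases: 0.13 and 0.51, rates 5.2% and 8.0%.

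For a fixed 30-point gap with c = 0.5 and ρ = 0.5, the change-score variance is 1 + 0.25 × (0.21 + 0.24)/2 = 1.056, so SE = √(2 × 1.056/n) = 0.325, 0.230 and 0.188 at n = 20, 40 and 60. Bias/SE is 0.15/SE = 0.46, 0.65 and 0.80. The false-positive rates are about 7.5%, 10% and 12.6% by the normal approximation, and simulations with a t reference agree closely.

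**The case against.** The strongest reply is that the flaw is inferred: the document does not say that main effects were used. If covariate-by-time terms, change scores, ANCOVA on follow-up or weighting were used, the concern falls away. That stands, and it is why the point is conditional. But the listed model has no covariate-by-time term, and adding two covariates to it in the ordinary way gives main effects. As written, a reader cannot tell an informative check from an empty one.

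Exact cancellation also needs an identity link, complete pairs and a model saturated in group and time. The first two are not established: PROC GLIMMIX handles other distributions, and the analysis set is fixed at baseline. The runs above show that relaxing them moves the DID slightly and leaves most of the bias. On saturation, the listed terms include no group main effect. Under a common-baseline coding, main-effect adjustment would move the estimate (0.255 to 0.151 SD in one run at 50 per group). That coding conflicts with the stated effect formula, which uses separate group baselines, and with the four cell means.

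The sentence covers more than the DID. Group differences at each visit do respond to main-effect adjustment: in the complete-pair simulation the baseline difference went from 0.154 to −0.069. So the sentence is informative for those contrasts, but they are not the stated treatment effect.

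The magnitude rests on assumptions, its low end is negligible, and the direction is unknown: confounding could as easily hide an effect as create one. All of that stands.

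Finally, stability under covariate-by-time adjustment is itself a weak test: 47% vs 14% is a ratio of about 3.4, falling to about 2.2 (39% vs 18%) with 30% missing. That is a reason to report the adjusted estimate and its interval rather than a verdict on stability.

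**Conclusion.** The concern holds as a conditional statement. If race/ethnicity and education entered as main effects, the reported stability of the DID is guaranteed in a linear model with complete pairs. It is nearly so in the scenarios examined with randomly missing follow-up or a logit link. It is then little or no evidence that these imbalances do not explain the effect.

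This does not show that confounding exists, or that the reported sentence is false. The bias in this trial cannot be computed. At the Chi-square threshold for imbalance, with an assumed covariate effect on change of 0.2 to 0.5 SD and within-person correlation of 0.3 to 0.7, it runs from 0.13 to 0.63 standard errors, a false-positive rate of 5.2% to 9.7% against a nominal 5%. The conclusion rests on main-effect entry, which is likely but not stated, and on a separate mean for each group and visit, which the effect formula supports. This is a cheap improvement and not a demonstrated analysis error.

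**What to change.** - Repeat the adjusted analysis with race/ethnicity-by-time and education-by-time terms, or regress the 12-week change on group and these two covariates. ANCOVA on follow-up or weighting would also serve.
- Replace the statement of no material change with the unadjusted and adjusted DIDs side by side, each with a 95% confidence interval.
- State how the covariates entered, the distribution and link for each outcome, and the number with both visits in each group.
- If such an adjustment was already used, say so and show both estimates; nothing more is needed.

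The data are already collected, so the work is a few SAS terms and a short table. The price is some precision. For assumed group sizes of 60, 40 and 20, the standard error of the DID rises about 5%, 5% and 7% with two binary covariates (8%, 8% and 10% if they do not affect change), and about 8%, 10% and 13% with two three-level covariates. The change deals only with these two measured covariates, not with the staggered start or unmeasured differences between the groups.
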